10.5.2.2. Cosmesis and Function at 24 Months from Wound Closure

For the purpose of the main analysis, all values (both on-site and remotely collected) will be used, with missing values imputed as described in SAP Section 10.1.4.2.

For the purpose of the sensitivity analysis, to explore the possible influence of remotely captured data, the following procedure will be applied:

- 1. Repeat step 3a from the above section (10.5.2.1) for additional follow-up time points 18 months and 24 months, to get the "corrected" *remote* evaluations.
- 2. Impute missing MVSS values at 24 months, applying the imputation procedure from SAP Section 10.1.4.2 on observed on-site evaluations and "corrected" remote evaluations from all previous time points (for time points up to 12 months previously "corrected" remote evaluations can be used).

10.5.2.3. Exploratory Analyses of MVSS and POSAS

For the purpose of exploratory analyses of MVSS (see SAP Sections 11.1.6.8 and 11.2.5.2) and POSAS (see SAP Sections 11.1.6.7 and 11.2.5.1) all observed values (both on-site and remotely collected) will be used.

11. Statistical Analysis of Target Variables

The analysis is planned to be carried out in two stages, as described below.

- 1. The first analysis will be performed at the end of the 12 months follow up period. This analysis will be the only inductive analysis of the trial and will include statistical tests for the primary and secondary endpoints as described above, as well as 12 months safety endpoints. At this time-point, data will be available for all patients on the primary and secondary end-points, as well as the 12 months safety endpoints. Missing values for early drop outs etc. will be handled as described in Sections 10.1 and 10.2. The complete data set documented so far will be locked and analyzed as described above. The 24 months data, although captured in the eCRF for a few of the subjects at the stage of end of the 12 months follow up period, will not be included, revealed or analyzed during these analyses.
- 2. The second and final analysis covers the data of the full 24 months safety follow up. It will be conducted after the last patient has reached the 24 months assessment, 12 months after first stage of analysis. At this analysis, all accumulated safety endpoints at the 24 months follow up will be evaluated.

Long term follow up assessments of Cosmesis (MVSS and POSAS), quality of life (EQ5D and BOQ) and functionality (LEFS, QuickDASH and ROM) will be performed by a "blinded assessor". The assessor signs a "blinded assessor memo" which describes the procedures required to maintain the investigator blinded from the treatment arm. The blinded assessor will remain blinded throughout the whole duration of the trial.

The data sets for analysis will be 100% source document verified and signed by the site investigator. Therefore, data changes are prevented during the further conduct of the study. Data management quality control actions will ensure that data used in the analysis is not changed afterwards (see the Data Management Plan for further details).

For a better overview of this SAP, the statistical analysis of target variables described below will be displayed separately for these 2 stages of analyses.

All variables not mentioned explicitly in the following will be analyzed descriptively (as part of the case-wise listing).

Unless otherwise specified, all statistical tests will be conducted against a two-sided alternative hypothesis, employing a significance level of 0.05.

11.1. First Stage Analysis -12 Months Follow Up

11.1.1. Demographics Data and Other Baseline Characteristics

For all considerations regarding the demographics and other baseline characteristics the full analysis set will be used.

The following demographic and baseline information will be tabulated:

- Age Group
- Age
- Gender
- Ethnicity
- Race
- Height (cm)
- Weight (kg)
- BMI
- Physical examinations (categorized as normal, abnormal-NCS, abnormal-CS, not done):
 - Head, eyes, ears, nose and throat (HEENT)
 - Respiratory system
 - Cardiovascular system
 - Abdomen
 - Musculoskeletal / Extremities
 - Neurological
 - Lymph Nodes
- Vital signs:
 - Temperature
 - Heart rate
 - Respiratory rate

- Systolic and diastolic blood pressure (mmHg)
- Assessment of vital signs (normal, abnormal-NCS, abnormal-CS)
- Pain assessment:
 - FPS-R
 - Assessment of pain (normal, abnormal-NCS, abnormal-CS)
- Local laboratory:
 - Diabetes status (yes/no)
 - HbA1c (%)
- Burn history (on a patient level):
 - Time since injury to randomization (hours)
 - Etiology of injury (Fire/Flame, Scald, Contact)
 - Place of injury (Outdoors, Indoors, Car, Other)
- General wound description (on a wound level):
 - Anatomical location (face, head, neck, etc.)
 - %TBSA of 2° SPT Burns (clinical assessment)
 - %TBSA of 2° DPT Burns (clinical assessment)
 - %TBSA of 3° FT Burns (clinical assessment)
 - Information whether escharotomy had been performed prior to randomization
 - Eschar description (white, moist, dry, etc.)
 - · Information whether cleansing was performed
 - Information whether all superficial keratin (blister) were removed from wound
- Target wound description (assessments at screening):
 - General wound description (see above; on a wound level; for target wounds only)
 - Information whether the wound was treated prior to enrollment (TWs)
 - Treatment of TWs prior to enrollment (SSD, lodine, etc.)
- Target wound description (on a patient level, assessments at screening):
 - Total wounds %TBSA
 - TWs DPT total area (%TBSA) (clinical assessment)
 - TWs FT total area (%TBSA) (clinical assessment)

- Overall TWs depth per patient (all full thickness, mixed, all deep partial thickness) (clinical assessment)
- Overall TW area (SPT+DPT+FT) (clinical assessment)
- Criteria for inclusion (met/not met)
- Counts of patients/wound per strata (%TBSA cut point 15%, % FT burns cut point 20 %, center)

All the above baseline information will be presented using descriptive statistics by treatment group and in total.

If any of the baseline factors gender, percent SPT area (the area of SPT as a percentage of the total area of all TWs, classified as <25% or \geq 25%), time from injury to randomization or number of TWs (1, 2, 3-4, \geq 5) are found to be significantly different between the treatment groups at the 15% level (Chi-squared tests (or in case of small estimated cell counts Fisher's exact test) for categorical variables and one-way analysis of variance for continuous variables) then the factor will be included as an extra adjusting covariate in the supportive analysis models for the primary and secondary efficacy endpoints.

Furthermore, a table for the disposition of patients will be produced.

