11.1.3. Primary Efficacy Analysis: Time to Complete Eschar Removal

The primary efficacy variable will be analyzed using the FAS. Missing data for the main primary analysis and for the three sensitivity analyses will be handled by the methods described in Section 10.1.2. In addition, the primary analysis will be repeated for the PP collective as sensitivity analysis.

Time until complete eschar removal will be defined as the time until complete eschar removal has been achieved for all TWs. This will be measured as time from the randomization date (days). Kaplan-Meier curves will be presented graphically to display the distribution of time to complete eschar removal under the two treatments. Median time to complete eschar removal

will be estimated for each treatment group with a 95% confidence interval. Furthermore, descriptive statistics for time to complete eschar removal will be presented. The treatment groups will be compared using a Cox regression model. The comparison will be adjusted for clinical center, age, %TBSA, proportion of the FT area of a patient and number of TWs (1,2,3-4, ≥5) by including each of them in the Cox regression model together with the treatment variable (NexoBrid vs. SoC). The treatment groups will be compared by testing the null hypothesis of no difference, comparing the ratio of the estimated treatment coefficient to its standard error to a standard normal distribution.

The Cox Regression analysis outlined above will be performed if the proportional hazards assumption appears to hold. This will be checked by including in the regression model a variable representing the interaction between time since randomization and treatment group. This coefficient will be tested (on actual sample allocation, without the re-randomization test) to be nonzero. Additionally, a log likelihood test comparing the model fit of a model with all time by covariate interactions added with a model without these interactions will be computed. The proportionality assumption will be rejected if one of these tests yields a significant result at the 10% level. In this case, we will use a generalized Wilcoxon-Gehan test. The Wilcoxon-Gehan test will be performed using the Wilcoxon option (also provided by default) in the SAS procedure PROC LIFETEST using the following SAS Code:

```
PROC LIFETEST DATA=burn_data;
TIME time*status(0);
STRATA agegroup ftgroup numtw tbsagroup centergroup / GROUP = treatment_group;
RUN;
```

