Here burn_data is the data set containing all necessary information. The variable time is the time to complete eschar removal, status is a censoring variable (0 for censor and 1 for complete ER event) and agegroup, ftgroup, numtw, tbsagroup, and centergroup are the variables, which the model is adjusted for. Agegroup, ftgroup, tbsagroup and centergroup are the stratification levels defined in Section 11.1.11 and numtw is the number of target wounds $(1, 2, 3-4, \ge 5)$.

Supportive analyses will include adjustment for other baseline variables that are imbalanced, based on the analyses described in Section 11.1.1.

The comparison between treatments will also be conducted on the time to complete eschar removal measured from the date of ICF as an additional analysis.

As an additional analysis, time to complete eschar removal will be analyzed on a target wound level using a method of survival analysis with clustered data that is based on appropriate assumptions. By "clustered data", we refer to the multiple target wounds that can occur in a patient. The proportional hazards assumption will be checked in the same way as in the patient level analysis. I.e. a Cox regression model will be fitted with covariates treatment, center, age, %TBSA, proportion of the FT area of a patient, number of TWs (1,2,3-4, ≥5) and a variable representing the interaction between time since randomization and treatment group. The latter coefficient will be tested to be nonzero. Additionally, a log likelihood test comparing the model fit of a model with all time by covariate interactions added with a model without these interactions will be computed. The proportionality assumption will be rejected if one of these tests yields a significant result at the 10% level. If the proportional hazards assumption is appropriate we will use a marginal Cox regression analysis with a robust sandwich estimator. If not, then we will use a parametric frailty model. Either method can be implemented in SAS (see Gharibvand and Liu, 2009 for details). The marginal Cox regression model is implemented in the PHREG procedure and the robust variance option is implemented by specifying the COVS(AGGREGATE) option. This induces the use of the robust variance method of Binder et. al. [22]. The parametric frailty model will be implemented using the following SAS-code:

```
PROC PHREG DATA=burn_data;

CLASS Subject_id treatment_group centergroup numtw;

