where subject_ID is a unique identification number for each patient, time is the time to wound closure on a wound level. Censor is a censoring indicator, treatment_group gives the treatment group, age1-age3 are indicator variables for a subject being in age group A1 − A3 respectively (per age groups defined in Section 11.1.11), ft1is an indicator for a subject with proportion of the FT area <20% out of the total burned area (group C1, defined in Section 11.1.11), TBSA1 is an indicator for a subject with overall %TBSA in (1% to 15%), inclusive (group B1, defined in Section 11.1.11), number_tw2 is an indicator variable for the subject having 2 target wounds (patient level), number_tw3 is an indicator variable for the subject having 3-4 target wounds (patient level), number_tw4 is an indicator variable for the subject having ≥5 target wounds (patient level), US, EEU and WEU are indicator variables for the individual being in region US, EEU and WEU (patient level) and burn_data is a SAS data set containing the required information.

Kaplan-Meier curves will be presented graphically to display the distribution of time to complete wound closure under the two treatments.

If any of the baseline factors are found to be significantly different between the treatment groups (based on the analyses described in Section 11.1.1), then the factor will be included as an extra adjusting covariate in a supportive analysis of time to complete wound closure.

As an additional analysis, the time to complete wound closure will be analyzed on a subject level. Kaplan-Meier curves will be presented graphically to display the distribution of time to complete eschar removal under the two treatments on a subject level. Median time to complete eschar removal will be estimated for each treatment group with a 95% confidence interval. Furthermore, descriptive statistics for time to complete eschar removal will be presented. The treatment groups will be compared using either a Cox regression model (if the proportional hazards assumption appears to hold), or a generalized Wilcoxon-Gehan test (if the proportional hazards assumption does not hold), as described in Section 11.1.3 for the main analysis of the primary efficacy endpoint.

As supportive analyses, the time to reach 100% wound closure will be analyzed on a wound level (similar to the main analysis outlined above) and on a subject level (similar to the additional analysis outlined above).

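### Extra covariates for the supportive models are chosen by a between-arm test at the 15% level instead of being fixed in advance for their expected prognostic value

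*SAP*

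**What the plan says.** SAP 11.1.1 opens the rule with "If any of the baseline factors gender, percent SPT area" (split at 25%), "time from injury to randomization or number of TWs" (four classes). Each factor is compared between arms, by chi-squared or Fisher test if categorical and by one-way analysis of variance if continuous. If any "are found to be significantly different between the treatment groups at the 15% level", "then the factor will be included as an extra adjusting covariate in the supportive analysis models for the primary and secondary efficacy endpoints". Association with the outcome is not a criterion.

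Other sections rely on the rule. In 11.1.3: "Supportive analyses will include adjustment for other baseline variables that are imbalanced". Sections 11.1.4.1 to 11.1.4.4 refer back to it in the same way for each secondary endpoint. Section 11.1.5.1 extends it to a supportive wound-closure analysis: "If any of the baseline factors are found to be significantly different between the treatment groups".

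The main analyses have a fixed covariate set. For the primary endpoint, "The comparison will be adjusted for clinical center, age, %TBSA, proportion of the FT area of a patient and number of TWs", "by including each of them in the Cox regression model together with the treatment variable". Surgical excision (11.1.4.1), both autograft endpoints (10.1.3.3, 11.1.4.4) and wound closure (11.1.5.1) have the corresponding set. The blood-loss model (10.1.3.2) has center, %TBSA, FT proportion and age, but not number of target wounds.

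**The concern.** Under random allocation a baseline comparison can detect only chance. What moves the estimate in a given trial is the imbalance multiplied by the factor's prognostic strength. The rule looks at the first and ignores the second: a strong predictor at p = 0.16 stays out, and an irrelevant factor at p = 0.10 goes in.

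The SAP treats two of these factors as possible predictors elsewhere. Sex is always in the imputation model for autograft area (10.1.3.3), and the SPT proportion, undichotomised, is always in the Method 2 imputation model for blood loss (10.1.3.2). Time from injury is a plausible third. The primary clock starts at randomization, and the protocol's inclusion criteria allow consent up to 84 hours after injury, so patients can enter that clock at quite different stages.

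At stake is the usefulness of the supportive analysis. It should show whether the result survives adjustment for other plausible predictors. As written, chance decides whether that analysis exists and which covariates it holds. For number of target wounds the rule changes nothing except in blood loss, because the other models already contain it.

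**Working it through.** **Inputs.** Entry threshold 0.15 (SAP 11.1.1); 145 patients enrolled (13.3); 1:1 allocation (11.1.11); two-sided 5% level (11.1.9). The documents give no correlation between these factors and any outcome, so r is an assumption, taken from 0.1 to 0.5. It means the partial correlation left after the covariates already in the model. The SAP gives no operating figure for the rule, so there is none to reproduce.

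**1. How often nothing is added.** A factor balanced by chance misses the cut with probability 0.85. With independent factors:
- gender, percent SPT and time from injury: 0.85³ = 0.614, about 61% of trials;
- blood loss, with number of target wounds as a fourth: 0.85⁴ = 0.522, about 52%.

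**2. Largest imbalance that escapes.** The critical value is z = 1.44. At N = 145 this is 1.44 × √(4/145) = 0.24 SD, or about 12 percentage points for a binary factor with 50% prevalence.

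**3. What that leaves in the estimate.** The conditional shift is at most 1.44 × r standard errors, in either direction:

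| Assumed r | Maximum shift (SE) |
|---|---|
| 0.1 | 0.14 |
| 0.3 | 0.43 |
| 0.5 | 0.72 |

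**4. Error rate at the cut, and on average.** With Z the test statistic, the one-sided error given an imbalance u is P(Z > (1.96 − r·u)/√(1 − r²)), against a nominal 2.5%.

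| r | u = +1.44 | u = −1.44 | Mean over unflagged trials (−1.44 < u < 1.44) |
|---|---|---|---|
| 0.3 | 5.5% | 0.6% | 2.25% |
| 0.4 | 6.5% | 0.3% | 2.06% |
| 0.5 | 7.6% | 0.1% | 1.82% |

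The average is below 2.5% throughout.

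**5. Simulation, one candidate covariate, N = 145, simple 1:1 allocation.**

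Linear model (20,000 runs, true effect 0.5 SD for power):

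| r | Power: always adjust | Power: 15% rule | Two-sided type I error: always | Two-sided type I error: rule |
|---|---|---|---|---|
| 0.3 | 87.6% | 85.6% | 4.8% | 4.3% |
| 0.5 | 93.1% | 87.0% | 5.1% | 4.0% |

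The mean estimate under the rule was 0.500 to 0.501 for a true 0.5, so it is unbiased over randomization.

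Cox model (3,000 runs, about 65% events, covariate log HR 0.5 per SD, true treatment log HR 0.5): mean log HR 0.45 under the rule and 0.51 when always adjusting; power 59.7% and 69.6%. The SAP's target log HR is much larger in size (1.25, section 9.1.1), so these powers show the direction of the loss and are not a forecast for this trial.

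**The case against.** The strongest reply is that nothing confirmatory depends on the rule. Section 11.1.1 confines it to supportive models. The hierarchy in 11.1.9 and the re-randomization p-values in 11.1.2 belong to the main analyses, which always adjust for center, age, %TBSA and FT proportion, and for number of target wounds in all but blood loss. This stands, and it bounds the point.

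Four stronger readings are tempting, and the documents do not support them.
- A reader might infer that most trials would be left unadjusted. The 61% refers only to extra adjustment in a supportive model; the minimization factors are always in.
- A reader might take 5.5% to 7.6% as the error rate of the procedure. Those values need an imbalance exactly at the cut, favoring NexoBrid, and a correlation of 0.3 to 0.5. The opposite direction gives 0.6% to 0.1%, and the average is conservative.
- A reader might infer a biased estimate. The shift is conditional on the realised imbalance; over randomization the linear estimate is unbiased.
- A reader might turn the precision gain into patients: 145/(1 − r²) − 145 gives about 14 at r = 0.3, 28 at 0.4 and 48 at 0.5. That formula fits linear models on all 145 patients. The primary analysis is Cox or Gehan, and excision and autograft incidence are logistic. Autograft area uses only patients with a DPT target wound: at 62.6% of 145, about 91 patients, the gain is about 9, 17 and 30. Blood loss is linear only if normality is not rejected.

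The correlations are also unsupported by the documents, and at r = 0.1 little is lost.

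A practical objection also stands. Simply adding continuous covariates does not work in every branch. If proportional hazards is rejected, the primary analysis becomes a stratified Gehan-Wilcoxon test, and the power update in 13.3 anticipates this because it happened in MW2010-03-02. Blood loss may become a stratified Wilcoxon test. Neither takes a continuous covariate, so the fix must cover both.

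None of this gives a reason to select covariates by a between-arm p-value.

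**Conclusion.** The concern holds as an improvement to the supportive analyses, not as a threat to the confirmatory result. The 15% rule selects on chance imbalance and ignores prognostic value. It leaves the supportive model without extra covariates in about 61% of trials (52% for blood loss), if the candidates are independent. What remains uncorrected in a single trial is at most 1.44 × r standard errors. Over repeated trials the cost is some precision, a slightly conservative supportive test and attenuation of the Cox log hazard ratio. The size rests entirely on the assumed r and on the simulated settings, which use simple allocation in place of minimization.

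**What to change.** Delete the 15% tests as a selection rule. In SAP 11.1.1, 11.1.3, 11.1.4 and 11.1.5.1, state that one pre-specified supportive regression model per endpoint always adds:
- gender;
- percent SPT of target-wound area, continuous;
- time from injury to randomization, continuous;
- number of target wounds, for blood loss only (the other models already have it).

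State also that where the main analysis falls back to a stratified Gehan-Wilcoxon or Wilcoxon test, the supportive adjusted result still comes from a regression that can take these covariates. Examples are a Cox model with robust variance, read as an average hazard ratio, and rank-based analysis of covariance for blood loss. The wound-level frailty fallback in 11.1.5.1 already accepts covariates.

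The cost is SAP wording, three or four model terms and the programming of the two fallback regressions. The factors are already collected or derived (7.2.1, 10.3.1.7, 11.1.1), and the main analyses do not change.

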11.1.2. Re-Randomization Test

Treatment allocation will be performed in this trial by minimization, therefore the p-values reported in this trial for the main analyses of the primary and secondary endpoints, performed on the FAS, will be based on the re-randomization test. To note, all other analyses (sensitivity, supportive, additional), including analyses on PP population, will be performed without the rerandomization test.

The re-randomization test is advocated by Proschan et al (Biometrics 2011; 67:1135-41) for trials that employ minimization, and belongs to the class of tests that are based on permuting the treatment allocations of the patients.

The test works as follows. Suppose the analysis for an endpoint is performed as described in Sections 11.1.3 or 11.1.4 below and a p-value for the estimated treatment difference is p*. We now return to the list of patients in the same order as they entered the trial and re-apply the minimization procedure to their treatment allocation, as described in Appendix 13.1. Because

the procedure involves random allocations at various junctures during the trial, the next time we apply the procedure it will in general yield a different set of treatment allocations for the patients. Having obtained these new treatment allocations, we then re-analyze the data as if these had been the true treatment allocations, and obtain a new p-value p_1 and corresponding test statistic s_1 for the test of the treatment difference. We repeat this step a large number of times (in this trial we will use 8000 repeats) and obtain a set of 8000 pairs of p-values and test statistics (p_1 , s_1), (p_2 , s_2), ..., (p_{8000} , s_{8000}). If exactly n of these 8000 p-values are less than or equal to the value p^* (obtained on the real data) with the test statistic in the direction of advantage to NexoBrid, then the re-randomization test p-value is assigned the value 2*n/8000.

The random seed for the re-randomization will be 48920.

Following teleconference with the FDA on April 2017, it was decided that the form of the minimization used for treatment allocation in the trial will be modified from strict minimization (without a random element) to minimization with a random element. The re-randomization test can naturally accommodate this modification. When re-allocating treatments for this re-randomization analysis, those patients allocated treatment in the trial using strict minimization will be re-allocated treatment using strict minimization, while those patients who entered later and were allocated treatment using minimization with a random element will be re-allocated treatment using minimization with a random element.

The minimum and maximum numbers of patients allocated to each treatment group over the 8000 re-randomized samples will be reported.

